## 7.3 LOST TO FOLLOW-UP

A participant will be considered lost to follow-up if he or she fails to return for two scheduled visits and study staff are unable to contact the participant after at least 3 attempts.

The following actions must be taken if a participant fails to return to the clinic for a required study visit:

- The site will attempt to contact the participant, reschedule the missed visit within 2 weeks, counsel the participant on the importance of maintaining the assigned visit schedule and ascertain if the participant wishes to and/or should continue in the study
- Before a participant is deemed lost to follow-up, the investigator or designee will make every effort to regain contact with the participant (where possible, 3 telephone calls and, if necessary, a certified letter to the participant's last known mailing address or local equivalent methods). These contact attempts will be documented in the participant's medical record or study file.
- Should the participant continue to be unreachable, he or she will be considered to have withdrawn from the study with a primary reason of lost to follow-up.

## 8 STUDY ASSESSMENTS AND PROCEDURES

### 8.1 ENDPOINT AND OTHER NON-SAFETY ASSESSMENTS

To screen for study eligibility, the research staff will use the EMR to review clinic schedules for new or returning patients with a physical appointment in the MUSC Head and Neck Tumor Center or telemedicine visit with a head and neck oncology provider who are potentially eligible for the study. Clinic rosters will be reviewed at a minimum of once per week, or more frequently if indicated by changes to the clinic schedule. As such, screening will generally be performed within 7 days of enrollment. After a patient who is potentially eligible for the study is identified, the patient will be contacted at the previously identified clinic visit (either physically within the MUSC Head and Neck Tumor Center or during the telemedicine visit) to discuss participation in the study as described below. The study coordinator who is screening the clinic schedule weekly will determine whether or not the potential trial participant has consented in EPIC to participate in research studies. For patients who have consented in EPIC to participate in research studies, the study coordinator will recruit using existing protocols for face-face clinic-based recruitment and study-specific documents to describe the study. For patients who have not consented in EPIC to participate in research studies, the head and neck oncology provider for the patient will notify the patient of the study and introduce the study to the potential participant. Following this introduction, if the potential participant is interested in learning additional information about the trial, the study coordinator will recruit using existing standard operating procedures for clinic-based or telemedicine-based recruitment. Patients who meet demographic and oncologic inclusion criteria will complete a screening BIS questionnaire; those with scores  $\geq 10$  will be eligible for the study. Those with scores  $< 10$  will not be eligible for the study, their BIS questionnaire will be shredded, and no personal information about the patient will be saved.

#### Primary Endpoint

Change in BIS scores. The BIS is a validated, 10-item patient-reported outcome measure (PROM) that assesses the affective, cognitive, and emotional aspects of body image due to cancer or its treatment over the prior 7 days. Responses include 'not at all', 'a little', 'quite a bit', and 'very much', and are scored from 0-3, respectively. Total BIS scores can range from 0-30, with higher scores indicating greater body image dissatisfaction. The BIS is a reliable PROM validated in oncology patients and has been widely used to study BID in patients with HNC.

#### Secondary Endpoints

##### *Behavioral Mediator*

Change in Body Image Coping Strategies Inventory (BICSI) scores. The BICSI is a 29-item validated measure of the cognitive and behavioral responses to manage threats to body image. BICSI contains three sub-domains; 1) appearance fixing (altering appearance by covering, camouflaging, or correcting the perceived defect), 2) avoidance (an attempt to escape or avert stressful body-image situations), and 3) positive rational acceptance (acceptance of the challenging event and positive self-care or rational self-talk about one's appearance). Items are scored on a 4-point Likert scale from 'definitely not like me' to 'definitely like me' (0-3). The scores for each subscale are calculated by summing the values for the individual questions and thus range as follows: 1) appearance fixing (0-30), 2) avoidance (0-24), 3) positive rational acceptance (0-33). For each subscale, higher scores indicate greater quantities of each conceptual domain (appearance fixing, avoidance, and positive rational acceptance). Avoidance and appearance fixing are maladaptive means of coping that are associated with dysfunctional schemas, elevated levels of BID and

distress, and poorer psychosocial functioning. Positive rational acceptance is a positive means of coping that is associated with lower levels of BID and distress.

*Clinical Activity*

Change in IMAGE-HN scores: The IMAGE-HN is a psychometrically sound, 24-item, multi-domain PROM consisting of 4 sub-scales and a global scale that can be used to measure key aspects of HNC-related BID due to HNC or its treatment. Responses include 'Never', 'Rarely', 'Sometimes', 'Often', 'Always', corresponding to a Likert scale of 0-4, respectively. Total IMAGE-HN scores on the global domain (21 questions) range from 0-84, with higher scores indicated greater HNC-related body image dissatisfaction. Raw scores for each sub-scale as well as the global scale can be converted to scaled scores for each, which range from 0-100 with higher scores representing greater HNC-related BID.

Response. Response is defined as a BIS score at 1-month post-intervention that is lower than the BIS score at baseline.

*Secondary Measures of Psychosocial Wellbeing*

Change in Shame and Stigma Scale scores. The Shame and Stigma Scale is a 20-item, validated, unidimensional PROM that measures four domains (shame with appearance, stigma, regret, and social/speech concerns) in patients with HNC over the prior 7 days. Responses include 'never', 'seldom', 'sometimes', 'often', and 'all the time' and are scored 0-4, respectively. The total score is calculated by summing the individual responses (except for 4 questions which are reverse scored) and thus ranges from 0-80. Higher scores reflect greater shame and stigma from HNC.

Change in PROMIS SF v1.0-Depression 8a scores. PROMIS SF v1.0-Depression 8a is a validated, 8-item measure developed by the NIH to assess self-reported negative mood, views of self, and decreased positive affect and engagement. Items are scored using a 5-point Likert scale from 'never' to 'always' (1-5). The total score is calculated by summing the individual responses and thus ranges from 8-40. Higher scores reflect more severe depressive symptoms.

Change in PROMIS SF v1.0-Anxiety 8a scores. The PROMIS SF v1.0-Anxiety 8a is a validated, 8-item measure developed by the NIH to assess self-reported fear, worry, and hyperarousal. Items are scored using a 5-point Likert scale from 'never' to 'always' (1-5). The total score is calculated by summing the individual responses and thus ranges from 8-40. Higher scores reflect more severe anxiety.

Change in PROMIS SF v2.0-Satisfaction with Social Roles and Activities 8a scores. PROMIS SF v2.0-Satisfaction with Social Roles and Activities 8a is a validated, 8-item, measure developed by the NIH to assess self-reported satisfaction with performing one's usual social roles and activities. Items are scored using a 5-point Likert scale from 'not at all' to 'very much' (1-5). The total score is calculated by summing the individual responses and thus ranges from 8-40. Higher scores reflect more severe anxiety.

Change in PROMIS SF v2.0-Social Isolation 8a scores. PROMIS SF v2.0-Social Isolation 8a is a validated, 8-item, measure developed by the NIH to assess self-reported perceptions of being avoided, excluded or unknown by others. Items are scored using a 5-point Likert scale from 'never' to 'always' (1-5). The total score is calculated by summing the individual responses and thus ranges from 8-40. Higher scores reflect more severe social isolation.

*Feasibility*

Intervention session duration is defined as the duration (in minutes) for each participant

Intervention session completion is the number of intervention sessions completed by each participant

Technical issues during tablet-based telemedicine sessions. Technical issues include inability to connect to the internet, video conference session, lack of video, lack of audio, insufficient tablet battery power, or any other technology related issues that prevents the session from otherwise functioning in a smooth and timely fashion.

Tablet return is defined as the receipt of the study-issued tablet by the study team within three months of the completion of the five sessions of the intervention.

Study dropout is defined as a participant voluntarily withdrawing from the study for whatever reason

#### *Acceptability*

Timing of Intervention will be assessed using a study-specific Likert scale measuring satisfaction with the timing of the intervention relative to the completion of treatment. Scores range from 0-5 with higher scores representing greater satisfaction with the timing of the intervention.

Method of Delivery of the Intervention will be assessed using a study-specific Likert scale measuring satisfaction with the method of delivery of the intervention. Scores range from 0-5 with higher scores representing greater satisfaction with the method of delivering the intervention.

Number of Intervention Sessions will be assessed using a study-specific Likert scale measuring satisfaction with the number of sessions of the intervention. Scores range from 0-5 with higher scores representing greater satisfaction with the number of intervention sessions.

Session content relevance will be assessed using a study-specific Likert scale measuring satisfaction with the content relevance of each session. Scores range from 0-5 with higher scores representing greater satisfaction with the content of the intervention.

Overall satisfaction will be assessed using a study-specific Likert scale measuring overall satisfaction with the intervention. Scores range from 0-5 with higher scores representing greater satisfaction with the intervention.

Likelihood of Recommending the Intervention will be assessed using a study-specific Likert scale measuring likelihood of recommending the intervention. Scores range from 1-5 with higher scores representing greater likelihood of recommending the intervention.

Working Alliance Inventory-Short Revised (WAI-SR) score. The WAI-SR is 12-item measure of working alliance consisting of three subscales assessing: 1) how closely client and therapist agree on and are mutually engaged in the goals of treatment (goals), 2) how closely client and therapist agree on the therapeutic tasks necessary to reach the treatment goals (tasks), and 3) the degree of mutual trust, acceptance, and confidence between client and therapist (bond). Patients score on a 5-point Likert scale ranging from rarely to always (1-5). Subscales scores for each of the subscales (goals, tasks, bond) range from 4-20. Total scores range from 12 to 60 with higher scores representing a stronger working alliance between the therapist and participant.

#### *Covariates*

Appearance Schemas Inventory-Revised (ASI-R) Score. The ASI-R is a psychometrically sound, 20-item measure of image investment. The ASI-R consists of two subdomains: Self-Evaluative Salience (of Appearance) and Motivational Salience (of Appearance). Items are scored using a 5-point Likert scale from 'strongly disagree' 'strongly agree' (1-5). Items 1, 4, 5, 9, 11, 12 are reverse scored. The composite ASI-R score is calculated as the mean of the 20 items, and thus composite ASI-R scores range from 1-5. The score for each subscale is also calculated as the mean of its included items. Higher scores reflect greater levels of image investment.

The individual's medical chart will be used to collect information performed as part of an individual's regular medical care are going to be used as a part of collection of trial data. As such, Health Insurance Portability and Accountability Act (HIPAA) rules, other relevant federal or state laws, and local institutional requirements will be followed, as applicable. The following information is to be obtained through review of existing data:

Demographics. Demographic characteristics include age, race, ethnicity, sex, marital status, living situation, insurance.

Clinical and Oncologic Characteristics. Clinical characteristics will include body mass index (BMI), comorbid medical conditions, and cancer history. Oncologic characteristics will include HNC tumor subsite, HNC tumor histology, American Joint Committee on Cancer TNM Class and overall stage grouping, type of ablative surgical, type of reconstruction, adjuvant radiation dose, adjuvant chemotherapy dose and agent, and time since completion of treatment.

## 8.2 SAFETY ASSESSMENTS

N/A

## 8.3 ADVERSE EVENTS AND SERIOUS ADVERSE EVENTS

### 8.3.1 DEFINITION OF ADVERSE EVENTS

This trial is considered to carry a low risk to subjects (i.e. has a "no more than minimal risk" designation). As such, this protocol defines an adverse event (AE) as any undesirable sign, symptom, medical, psychological, social, or emotional reaction that is definitely, probably, or possibly related to the study intervention.

### 8.3.2 DEFINITION OF SERIOUS ADVERSE EVENTS

A serious adverse event (SAE) will be defined as any undesirable sign, symptom, or medical condition which is fatal, is life-threatening, requires or prolongs inpatient hospitalization, results in persistent or significant disability/incapacity, is medically significant and which the investigator regards as serious based on appropriate medical judgment that is directly due to a study intervention. An important medical event is any AE that may not result in death, be life-threatening, or require hospitalization but may be considered an SAE when, based upon appropriate medical judgment, it may jeopardize the patient and may require medical or surgical intervention to prevent one of the outcomes listed in the definitions of SAEs.

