## 7 STUDY INTERVENTION DISCONTINUATION AND PARTICIPANT DISCONTINUATION/WITHDRAWAL

### 7.1 DISCONTINUATION OF STUDY INTERVENTION/EXPERIMENTAL MANIPULATION

At subject, PI, or study team member request.

When a subject discontinues from BRIGHT or AC but not from the study, remaining study procedures will be completed as indicated by the study protocol. If a clinically significant finding is identified (including, but not limited to changes from baseline) after enrollment, the investigator or qualified designee will determine if any change in participant management is needed. Any new clinically relevant finding will be reported as an adverse event (AE).

The data to be collected at the time of study intervention discontinuation will include the following:

- The reason(s) for discontinuing the participant from the intervention, and methods for determining the need to discontinue
- If the participant is due to complete assessments within 2 weeks of being discontinued from the study intervention, those assessments will be administered at the time of discontinuation; if the next scheduled assessments are more than 2 weeks from the discontinuation date, the discontinued

participant will wait for the next scheduled assessment. Thereafter, the participant will be included in all future scheduled assessments, even though not participating in the intervention.

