#### 8.3.3.2 RELATIONSHIP TO STUDY INTERVENTION/EXPERIMENTAL MANIPULATION

All AEs will have their relationship to study procedures, including the intervention, assessed by the PI based on temporal relationship and his clinical judgment. The degree of certainty about causality will be graded using the categories below.

- **Definitely Related** – There is clear evidence to suggest a causal relationship, and other possible contributing factors can be ruled out. The clinical event, including an abnormal laboratory test result, occurs in a plausible time relationship to study procedures administration and cannot be explained by concurrent disease or other drugs or chemicals. The response to withdrawal of the study procedures should be clinically plausible. The event must be pharmacologically or phenomenologically definitive.
- **Probably Related** – There is evidence to suggest a causal relationship, and the influence of other factors is unlikely. The clinical event, including an abnormal laboratory test result, occurs within a reasonable time after administration of the study procedures, is unlikely to be attributed to concurrent disease or other drugs or chemicals, and follows a clinically reasonable response on withdrawal.
- **Possibly Related** – There is some evidence to suggest a causal relationship (e.g., the event occurred within a reasonable time after administration of study procedures). However, other factors may have contributed to the event (e.g., the participant's clinical condition, other concomitant events). Although an AE may rate only as "possibly related" soon after discovery, it can be flagged as requiring more information and later be upgraded to "probably related" or "definitely related", as appropriate.

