### 8.3.5 ADVERSE EVENT REPORTING

All AEs, as defined above, will be collected and reported. Data collection will occur via electronic spreadsheet. The information will be saved in REDCap and managed by the study team. In consultation with the PI, a trained member of the study team will be responsible for conducting an evaluation of a SAE and shall report the results of such evaluation to the NIH and the reviewing Institutional Review Board (IRB) as soon as possible and in accordance with the reviewing IRB policy

---

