#### 9.4.4 SAFETY ANALYSES

N/A

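### AE and SAE relatedness thresholds do not match, Section 7.1 conflicts with Section 8.3.1 on what counts as an AE, and no by-arm summary of adverse events is planned

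*Combined protocol and SAP*

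**What the plan says.** All references are to the combined protocol and SAP.

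- **AE definition (Section 8.3.1).** An AE is a "reaction that is definitely, probably, or possibly related to the study intervention". The section gives the trial's minimal-risk designation as the reason.
- **SAE definition (Section 8.3.2).** The first sentence lists death, threat to life, hospital admission, disability and medical significance, and ends "which the investigator regards as serious based on appropriate medical judgment that is directly due to a study intervention". The second sentence then says: "An important medical event is any AE that may not result in death, be life-threatening, or require hospitalization but may be considered an SAE".
- **Causality grading (Section 8.3.3.2).** "All AEs will have their relationship to study procedures, including the intervention, assessed by the PI", and "The degree of certainty about causality will be graded using the categories below". The categories are definitely, probably and possibly related.
- **Collection and reporting (Sections 8.3.5 and 8.3.6).** "All AEs, as defined above, will be collected and reported". SAEs are evaluated and the result is reported to the NIH and the IRB.
- **Findings after enrolment (Section 7.1).** "Any new clinically relevant finding will be reported as an adverse event (AE"), with no relatedness condition attached.
- **Schedule and analysis.** The schedule in Section 1.3 places AE/SAE assessment at Visits 2 to 9. Section 9.4.4, headed "SAFETY ANALYSES", is marked N/A, as is Section 8.2. Section 10.1.6 provides a monthly aggregate review by the PI.

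**The concern.** The SAE definition triggers evaluation and onward reporting, so staff must be able to apply it without guessing. Here the AE threshold, the SAE threshold and the causality scale use different terms, and two sections disagree on whether relatedness is needed before a finding becomes an AE at all.

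The issue bears on this trial's own stated risks. Section 2.3.1 names psychological distress as one of its two primary risks, and Section 2.2.1 cites raised suicide mortality in this population.

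Relatedness is also graded with knowledge of arm. Section 4.1 describes a non-blinded trial, and Sections 6.1.2.1 and 6.1.2.2 contrast psychologist-delivered therapy with stored videos. If that grade also decides what is recorded, counts could differ between arms for reasons other than harm.

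Finally, Section 4.2 says that the trial prepares for a definitive randomised trial. A by-arm account of events would be a natural output, and none is planned.

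**Working it through.** No arithmetic applies, and the plan gives no figure to reproduce. The check is to read the sections against each other.

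**Step 1: what does the closing phrase of Section 8.3.2 govern?** The sentence allows two readings.

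- Reading A: the phrase governs every criterion in the list. This is the more literal reading.
- Reading B: it governs only the last criterion, medical significance as judged by the investigator.

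| Event | AE under 8.3.1? | SAE, reading A | SAE, reading B |
|---|---|---|---|
| Death or hospital admission, possibly related | Yes | No | Yes |
| Death or hospital admission, unrelated | No | No | Yes |
| Neither death, threat to life nor admission, but may jeopardise the patient; possibly related | Yes | Can be (second sentence) | Can be (second sentence) |

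Under A, a grave event graded possibly related is an AE but fails the SAE test, while a less grave event with the same grade can pass through the second sentence. Under B, an unrelated death is an SAE although it is not an AE. On neither reading are SAEs simply those AEs that meet a seriousness criterion.

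**Step 2: can the SAE test be read off the causality scale?** No. Section 8.3.3.2 has three grades, and none corresponds to the wording of Section 8.3.2. Possibly related is the clearest failure under reading A. Whether probably related would qualify is not stated. A smaller mismatch is that Section 8.3.1 asks about relation to the intervention, while Section 8.3.3.2 grades relation to study procedures including the intervention. Section 2.3.1 says distress may arise from questionnaires, so the difference can matter.

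**Step 3: must a finding be related to be an AE?** Sections 8.3.1 and 8.3.5 together say yes. Section 7.1 says no. A finding reported under Section 7.1 but judged unrelated has no grade available in Section 8.3.3.2. The Section 7.1 sentence sits in a paragraph about participants who stop the intervention but stay in the study, so whether it reaches all participants is unclear.

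**Step 4: what happens to the events collected?** Assessments are scheduled at eight visits (Visits 2 to 9). No section of the statistical plan tabulates the events by arm, and the review in Section 10.1.6 is aggregate.

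**The case against.** The best defence is that this is a minimal-risk behavioural pilot, that a related-only definition was chosen for that stated reason, and that other routes catch what matters.

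- **Psychological events.** Section 2.3.3 sends cases of possible distress noted by staff to the PI, has these events reported to the IRB, and sets out steps for suicidality. Section 5.2 excludes people with suicidal ideation at entry.
- **Unanticipated problems.** Section 8.4.1 includes possibly related events, so a possibly related death could reach the IRB that way.
- **Distress by arm.** PROMIS depression and anxiety are measured at baseline, 1 month and 3 months, and Section 9.4.3 compares them between arms.
- **Missing unrelated grade.** Under a related-only definition, that category would be empty by design.

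Much of this stands, and it rules out three stronger conclusions that a reader might draw.

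1. That unrelated events are never recorded. Section 7.1 reports new findings without a relatedness test, and Section 7.2 puts reasons for leaving the study, including recurrence, second primary cancer and major surgery, on the CRF.
2. That a possibly related death is certainly not an SAE. That holds on reading A only.
3. That harms cannot be compared between arms at all. Average worsening in depression or anxiety would be examined.

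The defence does not remove the contradictions. A minimal-risk designation can justify light monitoring but not definitions that disagree. The unanticipated-problem route also requires the event to be unexpected and to suggest greater risk. Mean symptom scores do not replace a count of events. The empty-category argument fails once Section 7.1 admits findings that may be unrelated.

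**Conclusion.** The point holds as a conflict of definitions and a reporting gap. The relatedness tests for AEs and SAEs differ, and the SAE test is off the causality scale and at odds with the second sentence of its own section. Section 7.1 contradicts Sections 8.3.1 and 8.3.5, and no by-arm summary of adverse events is planned.

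The consequence that a grave, possibly related event misses SAE evaluation rests on reading A. The misfit between the definitions does not, since it appears on both readings. The concern about attribution made with knowledge of arm is a risk that the wording allows. The documents give no evidence that it has happened.

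The size cannot be put as a number, because the documents give no event rates. No sample-size, power or primary-endpoint figure changes. The matter should be corrected because these definitions trigger reporting to the NIH and the IRB and the correction is cheap, but it does not threaten the main result.

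**What to change.** 1. Reconcile Sections 7.1, 8.3.1, 8.3.2 and 8.3.3.2. Use one relatedness standard for AEs and SAEs, worded in the terms of the causality scale, and state whether it refers to the intervention or to all study procedures. Make the sentence structure of Section 8.3.2 show which criteria the standard governs.
2. State whether the Section 7.1 rule covers all participants, and make sure that any finding reportable under it can be graded, including as unrelated. Recording every event whatever its attribution is one way to do this. It is a debatable choice in a minimal-risk trial, and the correction does not depend on it.
3. Replace N/A in Section 9.4.4 with a descriptive table by arm of events and of participants with at least one event. No hypothesis test is needed.

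The cost is an amendment submitted to the IRB, one table and a few more entries for the coordinator. Section 9.2 refers to interim accrual data, so recruitment is already under way. A change in the recording rule would therefore mix two standards, and the table should note the date of the change.
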